24.3 Pharmacokinetic Analysis

A noncompartmental method of analysis will be used to analyze the plasma concentrations of pexidartinib. C_{\max} and the time to attain the C_{\max} (t_{\max}) will be determined directly from the observed data. The following PK parameters will be estimated, based on available data:

- Clearance
- Volume of distribution
- Area under the plasma/serum concentration-time curve (AUC)
- Elimination half-life

Pharmacokinetic assessments will be measured for each dose cohort of patients with correlations of C_{\max} and AUC to any SAEs. Dose-response trends in C_{\max} and AUC will be analyzed within each patient group for any suggestion of drug accumulation or alterations in PK based on concomitant medications.

24.4 Pharmacodynamic Analysis

No formal statistical analysis of pharmacodynamic endpoints will be performed. Pharmacodynamic data from each assay will be listed by dose. Possible relationships between PK and pharmacodynamic variables will be explored, as appropriate. Any biological activity will be described.

24.5 Statistical Analyses

Statistical analyses will be descriptive in general. Limited statistical comparisons for a dose effect may be made using analysis of variance. The dependent variables for assessing dose proportionality will be estimates of selected PK parameters.

No formal statistical analysis of data from the PRO instruments will be performed. Results for each instrument will be listed by dose. Change from baseline may be calculated, as appropriate. WOMAC data from patients with only upper extremity disease (e.g., PVNS of the elbow) may be excluded since WOMAC focuses on lower extremity function.

24.6 Sample Size and Power

The primary objective of the study is to assess the safety of pexidartinib in a limited number of patients with solid tumors. The number of patients is not based on statistical power considerations.

For the dose escalation phase of the study, 3 to 6 patients will be accrued per dose level in order to ensure the safety and tolerability. The probabilities of detecting DLTs in this study are shown in [Table 5](#) and [Table 6](#).

Table 5: Probabilities of Detecting DLTs (3 Patients)

Number DLTs in a Cohort of 3 Patients	Incidence of DLTs in Patient Population				
	0.10	0.20	0.30	0.40	0.50
0 ^a	0.729	0.512	0.343	0.216	0.125
1 ^b	0.243	0.384	0.441	0.432	0.375
2 or more ^c	0.028	0.104	0.216	0.352	0.500

^a Number of DLTs leads to advancing to the next cohort.

^b Number of DLTs leading to enrolling an additional 3 patients in the Cohort.

^c Number of DLTs leading to stopping the study and defining the MTD.

Table 6: Probabilities of Detecting DLTs (6 Patients)

Number DLTs in a Cohort of 6 Patients	Incidence of DLTs in Patient Population				
	0.10	0.20	0.30	0.40	0.50
0	NA	NA	NA	NA	NA
1 ^a	0.177	0.197	0.151	0.093	0.047
2 or more ^b	0.066	0.187	0.290	0.339	0.328

^a Number of DLTs leading to advancing to the next cohort [Prob (1 in first 3 and 0 in second 3)].

^b Number of DLTs leading to stopping the study and defining the MTD [Prob (1 in first 3 and 1 in second 3) + Prob (1 in first 3 and 2 in second 3)].

For the five disease-specific Extension cohorts, a sample size of 10 patients is considered the minimum sample size required to test the hypothesis that single agent pexidartinib can provide a clinical benefit in this patient population. For each Extension cohort, we plan to test the hypothesis of no clinical benefit against the hypothesis that at least 30% of patients achieve a clinical benefit. With a sample size of 10 patients per group, we will have 85% power at a 0.10 significance level to declare pexidartinib worthy of further study if at least 2 patients achieve clinical benefit. For this study, clinical benefit is defined as either CR/PR or PFS ≥ 6 months. If fewer than 2 patients achieve clinical benefit within a disease group, pexidartinib will not be considered worth of further study within that disease. Depending on the response in the 10-patient cohort, the sample size for a specific cohort may be increased by 30 additional patients (to approximately 40 patients total) if those data are determined to be necessary to design additional studies in that indication.

For the miscellaneous Extension cohort, a sample size of 20 patients will be used, as the tumor types are anticipated to be rare. The sample size is not determined by any statistical power considerations. Accordingly, the potential clinical benefit will be evaluated on a per-patient basis. If one or more partial responses are observed in patients in the miscellaneous cohort, additional patients (up to 20 total additional patients) may be recruited if needed to profile the tumor responses in the specific (or related) indications.

25.0 PRECAUTIONS

There is no previous experience with pexidartinib in humans. Although major adverse events are not anticipated, the investigator must proceed with utmost caution. Equipment, supplies, and properly skilled medical personnel must be immediately available for emergency use in the event of an unexpected reaction. Patients must be carefully selected and closely monitored.

For a complete description of preclinical studies reported during clinical studies with pexidartinib, please refer to the pexidartinib [Investigator's Brochure](#).

26.0 ADVERSE EVENTS

For safety information on pexidartinib, refer to the most recent version of the [Investigator's Brochure](#).

26.1 Definitions

An **adverse event** (AE) is any untoward, undesired, or unplanned event in the form of signs, symptoms, disease, or laboratory or physiologic observations occurring in a person given a test article in a clinical study. The event does not need to be causally related to the test article. An AE includes, but is not limited to, the following:

- Any clinically significant worsening of a preexisting condition.
- An AE occurring from overdose (i.e., a dose higher than that indicated in the protocol) of a test article, whether accidental or intentional.
- An AE occurring from abuse (e.g., use for nonclinical reasons) of a test article.
- An AE that has been associated with the discontinuation of the use of a test article.

Any treatment-emergent abnormal laboratory result which is clinically significant, i.e., meeting one or more of the following conditions, should be recorded as a single diagnosis on the adverse event page in the CRF:

- Accompanied by clinical symptoms
- Leading to a change in study medication (e.g., dose modification, interruption or permanent discontinuation)
- Requiring a change in concomitant therapy (e.g., addition of, interruption of, discontinuation of, or any other change in a concomitant medication, therapy or treatment)

A serious adverse event is an AE that:

- Results in death (NOTE: death is an outcome, not an event)
- Is life-threatening.

- Requires inpatient hospitalization or prolongation of an existing hospitalization.
- Results in a persistent or significant disability or incapacity.
- Results in a congenital anomaly or birth defect.
- Additionally, important medical events that may not result in death, be life-threatening, or require hospitalization may be considered SAEs when, based on appropriate medical judgment, they may jeopardize the patient and may require medical or surgical intervention to prevent one of the outcomes listed in this definition. Examples of such events include allergic bronchospasm requiring intensive treatment in an emergency room or at home, blood dyscrasias or convulsions that do not result in hospitalization, or development of drug dependency or drug abuse.

Disease progression is a study end point and clear progression or worsening of neoplasia should not be reported as an adverse event or serious adverse event. Findings that are *clearly* consistent with the expected progression of the underlying cancer should not be reported as an adverse event, and hospitalizations due to the progression of cancer do not necessarily qualify for a serious adverse event. Sudden and unexplained death should be reported as an SAE. If there is any uncertainty about a finding being due solely to progression of neoplasia, the finding should be reported as an adverse event or serious adverse event as appropriate.

Life-threatening refers to immediate risk of death as the event occurred per the reporter. A life-threatening experience does not include an experience, had it occurred in a more severe form, which might have caused death, but as it actually occurred, did not create an immediate risk of death. For example, hepatitis that resolved without evidence of hepatic failure would not be considered life-threatening, even though hepatitis of a more severe nature can be fatal. Similarly, an allergic reaction resulting in angioedema of the face would not be life-threatening, even though angioedema of the larynx, allergic bronchospasm, or anaphylaxis can be fatal.

Hospitalization is official admission to a hospital. An Emergency Room visit lasting longer than 24 hours should be considered a hospitalization. Hospitalization or prolongation of a hospitalization constitutes criteria for an AE to be serious; however, it is not in itself considered a serious adverse event (SAE). In absence of an AE, a hospitalization or prolongation of a hospitalization should not be reported as an SAE. This is the case in the following situations:

- The hospitalization or prolongation of hospitalization is needed for a procedure required by the protocol. Day or night survey visits for biopsy or surgery required by the protocol are not considered serious.
- The hospitalization or prolongation of hospitalization is part of a routine procedure followed by the center (e.g., stent removal after surgery). This should be recorded in the study file.
- Hospitalization for survey visits or annual physicals falls in the same category.

In addition, hospitalizations planned before the start of the study, for a preexisting condition that has not worsened, do not constitute an SAE.

Disability is defined as a substantial disruption in a person's ability to conduct normal life functions.

If there is any doubt about whether the information constitutes an SAE, the information is treated as an SAE.

Relatedness to study medication will be graded as either "probably", "possibly", or "unlikely", as follows:

Probably—The adverse event:

- Follows a reasonable temporal sequence from drug administration
- Abates upon discontinuation of the drug
- Cannot be reasonably explained by the known characteristics of the patient's clinical state

Possibly—The adverse event:

- Follows a reasonable temporal sequence from drug administration
- Could have been produced by the patient's clinical state or by other modes of therapy administered to the patient:

Unlikely—The adverse event:

- Does not follow a reasonable sequence from drug administration
- Is readily explained by the patient's clinical state or by other modes of therapy administered to the patient

A **protocol-related adverse event** is an AE occurring during a clinical study that is not related to the test article, but is considered by the investigator or the medical monitor (or designee) to be related to the research conditions, i.e., related to the fact that a patient is participating in the study. For example, a protocol-related AE may be an untoward event occurring during a washout period or an event related to a medical procedure required by the protocol.

Other Reportable Information: certain information, although not considered an AE, must be recorded, reported, and followed up as indicated for an AE. This includes:

- A case involving a pregnancy exposure to a test article, unless the product is indicated for use during pregnancy, e.g., prenatal vitamins. Information about use in pregnancy encompasses the entire course of pregnancy and delivery and perinatal and neonatal outcomes, even if there were no abnormal findings. If a pregnancy is confirmed, test article must be discontinued immediately in female patients. All reports of pregnancy must be followed for information about the course of the pregnancy and delivery, as well as the condition of the newborn. When the newborn is healthy, additional follow-up is not needed. Pregnancies occurring up to 3 months after completion of the study treatment must also be reported to the investigator.
- Overdose (e.g., a dose at least 40% higher than that indicated in the protocol). An overdose or incorrect administration of study drug is not an AE unless it results in untoward medical effects. Any study drug overdose or incorrect administration of study drug should be noted on the study drug administration CRF.
- Abuse (e.g., use for nonclinical reasons) with or without an AE.
- Inadvertent or accidental exposure with or without an AE.
- Device malfunction with or without an AE.

26.2 Recording and Reporting

A patient's AE or SAE can occur from the time the patient receives the first dose of study drug until the patient's End of Study visit.

The investigator must follow-up on all drug-related AEs, SAEs, and other reportable information until the events have subsided, returned to baseline, the patient has initiated any other anticancer treatment, or in case of permanent impairment, until the condition stabilizes.

All AE and SAEs must be recorded on source documents. All AEs and SAEs for patients who are not screen failures will be recorded in the CRFs.

AEs should be based on the signs or symptoms detected during the physical examination and on clinical evaluation of the patient. In addition to the information obtained from those sources, the patient should be asked the following nonspecific question: "How have you been feeling since your last visit?" Signs and symptoms should be recorded using standard medical terminology.

Any unanticipated risks to the patients must be reported promptly to the IRB/IEC.

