10.0 SELECTION OF STUDY POPULATION

All patients must participate in the consent process. During the consent process, the person obtaining consent must inform the patient of all elements of informed consent. No protocol-specific procedures, including screening procedures, are to be performed until the patient has signed and dated an institutional review board (IRB)/independent ethics committee (IEC)-

approved informed consent form. The study begins with the signing and dating of the informed consent form. Patients must also meet the inclusion and exclusion criteria to be enrolled in the study.

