18.0 SAFETY EVALUATION

Routine safety and tolerability will be evaluated from the results of reported signs and symptoms, scheduled physical examinations, vital sign measurements, 12-lead ECGs (including QTc intervals), and clinical laboratory test results.

Safety data will be reviewed by the investigator and the medical monitor. Safety of pexidartinib will be established after 28 days of dosing at the previous dosage group before the next higher dose is initiated.

More frequent safety evaluations may be performed if clinically indicated or at the discretion of the investigator. All AEs will be recorded from the time the patient receives the first dose of study drug until the patient's End of Study visit.

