22.0 TUMOR AND RELATED TISSUE COLLECTION

For patients who consent to this tumor and related tissue collection procedure, paired biopsies (where applicable) will be obtained to assess the effect of pexidartinib on PD endpoints and possibly pexidartinib concentration in the tissue (PK). The tumor lesions or fluids amenable to biopsy or extraction should not be target lesions. Patients will not be excluded from the study on the basis of consenting to biopsy. For patients' safety, soft tissue lesions such as skin or subcutaneous metastases will be preferentially selected for biopsy. Liver metastases will also be eligible for biopsy provided that it is considered feasible and safe in the opinion of a staff interventional radiologist. If there is a change in dose or clinical status after C1D15, one or more additional biopsies may be obtained to assess PD and PK information, in consultation with the Sponsor. If surgical resection of the tumor is performed within 12 weeks of the last dose of study treatment, details of the surgery and its outcome should be obtained. Tumor biopsy tissue may be submitted for biomarker analysis.

Where applicable, core biopsy samples should be obtained with an 18-gauge true-cut needle core biopsy device under ultrasound or computed tomography guidance. For cutaneous or subcutaneous lesions, a punch biopsy may be performed in place of a core biopsy. The tissue samples should be submitted fresh to the surgical pathology laboratory. If feasible, one half should be fixed in 10% buffered formalin and routinely embedded in paraffin, while the other half is to be snap-frozen to -70°C .

For samples including but not limited to pleural, peritoneal, cerebrospinal, or other fluids and tissues, please refer to the Sample Handling and Logistics Manual as well as [Attachment 2](#) and [Attachment 3](#).

For patients who consent to archival tumor tissue acquisition, the sample(s) will be obtained to generate baseline or historical evidence of target relevance.

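### AE and SAE capture opens only at the first dose, so a serious complication of a screening procedure is not reportable under Section 26.3, and Section 26.2 is inconsistent about screen failures

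*Combined protocol and SAP*

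**What the plan says.** The start of safety capture is stated three times, consistently:

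- Section 26.2: a patient's "AE or SAE can occur from the time the patient receives the first dose of study drug until the" End of Study visit.
- Section 18.0: "All AEs will be recorded from the time the patient receives the first dose of study drug", with the same end.
- Section 26.1 defines an AE as an event "occurring in a person given a test article in a clinical study".

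The flow charts match. The Adverse Events row is blank at screening. It begins at C1D1, or at C1D-7 for patients with a run-in.

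Other text looks to an earlier start:

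- Section 10.0: "The study begins with the signing and dating of the informed consent form".
- Section 26.2, shortly after the window: "All AEs and SAEs for patients who are not screen failures will be recorded in the CRFs". Source documents must carry all AEs and SAEs. Section 10.3 defines a screen failure as someone who consented but was not assigned treatment and did not receive test article.
- Section 26.1 has a category of protocol-related AE, with the example of "an untoward event occurring during a washout period or an event related to a medical procedure required by the protocol".

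Sections 13.1 and 14.1 both list an optional tumor biopsy at screening. Section 22.0 describes 18-gauge core biopsies and adds: "Liver metastases will also be eligible for biopsy provided that it is considered feasible and safe". Section 26.3 requires every SAE, whatever its cause, to reach the safety group within 24 hours of the site learning of it.

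**The concern.** The trial takes responsibility for a patient at consent but does not collect harm until the first dose. Between the two, it may do things to the patient that carry risk. The tumor biopsy is the clearest case, because it is done for the trial's pharmacodynamic and tissue pharmacokinetic purposes. If a patient bleeds after that biopsy and is admitted, a site that follows Section 26.2 literally has no SAE to report, and the sponsor may not hear of it through the safety system. If the patient then fails screening, the event would also be kept out of the CRF.

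What is at stake is the completeness of information on harm from study procedures, and the sponsor's ability to react to it. The screen-failure sentence makes matters worse: two sites could read Section 26.2 in opposite ways and both point to its text.

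**Working it through.** No statistical figure is involved. The check compares the provisions.

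**1. Length of the uncovered period.**
- Extension cohorts and escalation patients without a run-in: screening falls within the 21 days before C1D1 (Sections 13.1 and 14.1), and the first dose is on C1D1. Gap: up to 21 days.
- Run-in patients: screening runs from Day -28 to Day -7 in the flow chart, and the first dose is on C1D-7. Gap: 28 − 7 = 21 days, so about the same.
- The baseline tumor scan has its own 28-day window. That is a limit on the age of the scan, and I have not counted it as part of the gap.

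**2. The same complication at two time points.** Take a serious bleed after a tumor biopsy.

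| Test | Screening biopsy, before first dose | Repeat biopsy, C1D15 |
|---|---|---|
| Where allowed | Sections 13.1 and 14.1 | Sections 13.6 and 14.4 |
| Patient already given test article (26.1) | No | Yes |
| Inside the window (18.0, 26.2) | No | Yes |
| Adverse Events row marked in flow chart | No | Yes |
| 24-hour report (26.3) | Not triggered, because it is not an SAE | Triggered, whatever the cause |

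Procedure and outcome are identical; only the timing differs. For a patient who is dosed later, one might stretch the Section 26.1 definition to cover the event, but Section 26.2 still excludes it by date.

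**3. Other routes.** Section 26.2 sends unanticipated risks promptly to the IRB/IEC. That provision names neither the sponsor's safety group nor a 24-hour limit, and a recognized biopsy complication may not count as unanticipated.

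**4. Screen failures.** By Section 10.3 they receive no test article. By the window in Section 26.2, no event of theirs can be an AE or SAE. The CRF sentence in the same section nevertheless exempts their AEs and SAEs from the CRF. Under the stated window it exempts an empty set; it has a purpose only if capture begins earlier.

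**5. Effect on the analyses.** DLTs are counted in the first 28 days of treatment (Section 16.4), and the safety set is patients who received study medication (Section 24.1). Pre-dose events do not enter either the dose decisions or the efficacy analysis. However, Section 24.1 summarizes all AEs by dose group without restricting onset date. The first-dose window supplies that restriction at present, so it must be written in if the window is widened.

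**The case against.** The first-dose start is a deliberate and consistent choice: the AE definition, both statements of the window, the flow charts and the safety set all fit together. This stands, and it is why the main point is a gap in the rule; the contradiction is confined to the screen-failure sentence.

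Several stronger readings are tempting, and the documents do not support them.

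- A reader might infer that the protocol-related AE definition and the first-dose window cannot both be followed. They can. A protocol-related AE is a kind of AE, so it can be read as an attribution category within the dosing period, where it has content such as the repeat biopsy at C1D15.
- A reader might treat the interval after previous anticancer therapy as an uncovered washout. The 3 weeks in Section 10.2 are an eligibility criterion and may pass before consent. The design imposes no washout, and Section 26.1 mentions one only as an example.
- A reader might rest the case on that section's procedure example. It speaks of procedures that the protocol requires, whereas the screening biopsy is optional, and Section 22.0 prefers skin or subcutaneous lesions for safety. The gap does not depend on that example, because the window excludes every screening procedure, mandatory or not.
- A reader might conclude that nothing would be reported at all. The IRB/IEC route exists, and Section 26.1 resolves doubt in favor of an SAE. But that rule helps only where there is doubt, and the window leaves little.
- A reader might take 28 days as the gap in run-in cohorts, or multiply planned enrollment by the screening length. The first overlooks dosing on C1D-7. The second gives elapsed time, assumes that everyone uses the full window, and says nothing about expected events.

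**Conclusion.** The point holds as a gap in the stated safety rule and an inconsistency within Section 26.2. For up to 21 days before the first dose, in patients with and without a run-in, a serious complication of a study procedure is not reportable as an SAE under Section 26.3.

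The number of events affected cannot be estimated: the documents give neither the expected number of screening biopsies nor a complication rate, so a claim that harm is missed on any particular scale would go too far. Dose-escalation decisions and efficacy are not touched.

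The conclusion assumes that sites follow the window as written; a cautious site might report anyway, which would make capture uneven. The practical gain is limited to patients still to be screened. The recommended Phase 2 dose is already fixed and the text covers visits beyond Cycle 40, so many patients may already be past screening, but the documents do not state enrollment status.

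**What to change.** Reconcile Sections 18.0, 26.1 and 26.2 and the flow charts:

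1. From signed consent to first dose, record all SAEs and any AE judged related to a study procedure. Adapt the AE definition in Section 26.1 so that it admits these events in people not yet dosed.
2. Apply this to screen failures as well, and replace the sentence in Section 26.2 that keeps their events out of the CRF.
3. Report serious pre-dose events within 24 hours under Section 26.3.
4. Mark the Adverse Events row at screening, with a footnote on the limited scope before the first dose.
5. In Section 24.1, state that treatment-emergent summaries include only events with onset on or after the first dose, and list earlier events separately.

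From the first dose on, capture stays as it is. The cost is protocol and CRF wording and a small number of extra pre-dose reports. For patients already screened under the present rule, the study report should state that pre-dose procedure-related events were not systematically collected.
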